6.2.5 Incidence rate analysis

Follow-up adjusted incidence rate for the placebo-controlled period will be summarized by SOC and PT.

6.3 Clinical Laboratory Data

The following scheduled clinical laboratory parameters are to be assessed:

| | |
|--|---|
| Hematology | |
| Red blood cell count | |
| Hemoglobin | |
| Hematocrit | |
| Total leukocyte count, including differential | |
| Platelet count | |
| Serum Chemistry | |
| Aspartate aminotransferase (AST) | Total Protein |
| Alanine aminotransferase (ALT) | Albumin |
| Total bilirubin | Sodium |
| Direct bilirubin | Potassium |
| Alkaline phosphatase | Chloride |
| Lactate dehydrogenase (LDH) | Calcium |
| Creatinine | Phosphorus |
| Blood Urea Nitrogen (BUN) | Magnesium |
| Uric acid | Creatine kinase |
| Glucose | Thyroid stimulating hormone (TSH)- screening only |
| Urinalysis | |
| Protein | |
| Glucose | |
| Blood | |
| Leukocyte esterase | |
| Specific gravity | |
| pH | |
| Microscopic examination of the sediment if blood, protein or leukocyte esterase are positive on the dipstick | |
| Serology | |
| Serum for hepatitis C antibody, hepatitis B surface antigen (screening only) | |
| Other Analyses | |

| |
|--|
| INR |
| Prothrombin Time |
| Hemoglobin A1C (HbA1C)- screening only |
| Pregnancy test (WOCBP only: screening, predose, discharge). |
| Follicle stimulating hormone (FSH) (screening only for women only) |

Summaries of clinical laboratory data will be performed for scheduled laboratory parameters only. Listings of individual laboratory measurements by subjects for all the parameters, both scheduled and unscheduled, will be provided.

6.3.1 Quantitative analyses

Actual values, change from baseline and percent change from baseline will be summarized by visit for hematology, blood chemistry, coagulation (INR and prothrombin time), and the urinalysis parameters specific gravity and pH (actual values over time only). Number of evaluable subjects, mean, standard deviation, median, 25% and 75% quartiles, minimum and maximum values will be presented at each visit. Plots of mean values (with standard error) for actual values at each visit will be provided; mean values at timepoints where n < 20 will not be plotted.

Visit windows for by visit summaries

For laboratory by visit summaries, the analysis visit should be defined using visit windows (see Table 8).

Table 8 Visit Windows for Laboratory by Visit Summaries

| Analysis visit | Target visit day | Analysis visit window |
|---|------------------|--|
| Baseline | 1 | Most recent non-missing pre-dose value |
| Week 4 | 29 | [1 (post-dose only), 42] |
| Week 8 | 57 | [43, 70] |
| Week 12 | 85 | [71, 126] |
| Week 24 | 169 | [127, 210] |
| Week 36 | 253 | [211, 294] |
| Week 48 | 337 | [295, 350] |
| Week 52 | 365 | [351, the end day of the placebo-controlled period*] |
| * The end day of the placebo-controlled period is the last day before the first dose in OLE for subjects who enter OLE, and is the last day in study for subjects who do not enter OLE. | | |

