examination; NfL = neurofilament light chain; PK = pharmacokinetic; PSP = Progressive Supranuclear Palsy; PSPRS = Progressive Supranuclear Palsy Rating
Scale; RBANS = Repeatable Battery for the Assessment of Neuropsychological Disease Severity; SAE = serious adverse event; WOCBP = women of
childbearing potential.

^a Screening procedures may be conducted within 42 days prior to first dose unless otherwise specified.

CONFIDENTIAL

The information contained herein may not be used, disclosed, or published without the written consent of Biogen MA Inc.

Table 2: Double-Blind Procedural Outline

Procedure ^a	Week 0 (Day 1)	Weeks 4, 8, 16, 20, 28, 32, 40, 44 ^b (±3 days)	Weeks 12, 24, 36 (±3 days)	Week 48 (±3 days)	Week 52 (±3 days)	Early Discontinuation ^{c, d}	Notes
Eligibility Assessments							
Concomitant Medications	Review of concomitant medication as per Section 7.7.						
Safety Assessments							
Physical Examination	X		X		X	X	Predose.
Targeted Physical Examination	X	X	X	X	X	X	Postdose. Targeted, problem-focused physical examination performed at clinician's discretion (e.g., to evaluate any AEs).
Neurological Examination (NE)	X				X		Besides documenting signs of PSP, the NE should focus on any clinical evidence of increased intracranial pressure (e.g., history of headache, vomiting, or visual disturbances, and neurologic signs such as pupillary abnormalities and papilledema) that might contraindicate a lumbar puncture.
Physical Measurements	X		X		X	X	Weight only.
Vital Signs	X	X	X	X	X	X	Includes body temperature, respiratory rate, and seated BP and heart rate. BP and heart rate should be measured after the participant has been resting quietly for at least 5 minutes.
12-Lead Electrocardiogram (ECG)	X		See notes		X	X	Week 24 only.

CONFIDENTIAL

The information contained herein may not be used, disclosed, or published without the written consent of Biogen MA Inc.

Procedure ^a	Week 0 (Day 1)	Weeks 4, 8, 16, 20, 28, 32, 40, 44 ^b (±3 days)	Weeks 12, 24, 36 (±3 days)	Week 48 (±3 days)	Week 52 (±3 days)	Early Discontinuation ^{c, d}	Notes
Assess Infusion Site	X	X	X	X	X	X	
Laboratory Tests	X	See notes	X	X	X	X	Weeks 4 and 8 only.
Pregnancy Test	X	X	X	X	X	X	For WOCBP only (serum or urine - local/site) within 24 hours prior to dosing.
██████████ ██████████	■	██████████	■	■		■	██████████ ██████████ ██████████
Immunogenicity Assessments							

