5.1.1. Overall Study Design

The study design schematic is presented in [Figure 1](#). The study will consist of a 52-week double-blind treatment period, which will be followed by a long-term open-label extension period for follow up. Participants will be randomized to receive BIIB092 or placebo. Approximately 459 participants in total will be randomized in a 2:1 ratio to receive BIIB092 or placebo (306 participants active or 153 placebo). In the double-blind treatment period of the study, participants will be dosed approximately once every 4 weeks (Q4W) up to a total of 13 times, with the last dose of study treatment of the double-blind period (Dose 13) administered at Week 48.

At Week 52, participants completing the double-blind treatment period may choose to continue into the open-label extension period of the study. Participants who wish to continue in the open-label extension period will receive the first dose of the open-label study treatment at Week 52. Participants will be dosed approximately once Q4W throughout the duration of the open-label extension period. The duration of the open-label extension period will vary depending on the date of enrollment of the participant in the study. The study is expected to continue until BIIB092 is commercially available, the development program is terminated, or the study is terminated at the discretion of the Sponsor, whichever comes first.

CONFIDENTIAL

The information contained herein may not be used, disclosed, or published without the written consent of Biogen MA Inc.

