17.4.2. Safety Analyses

Safety analyses will be performed by as-treated treatment group for treated participants. Safety endpoints include the frequency and proportion of participants with AEs, SAEs, AEs leading to discontinuations and deaths, and other significant AEs reported on case report forms. Other safety endpoints include laboratory abnormalities, changes in laboratory parameters, changes in vital signs, physical findings, and ECGs.

In general, AE presentations will be by system organ class and preferred term.

The primary safety analyses will be for comparative safety of BIIB092 to placebo in the double-blind treatment period. Safety endpoints will include data up to the start of the open-label extension period for participants who completed the double-blind treatment period and continue into the open-label extension, or up to last dosing date plus 30 days for participants discontinuing study treatment during the double-blind treatment period.

Additional safety analyses will include all events reported through the time of database lock for the cumulative BIIB092-treated participants. Safety endpoints will include data from the first dose of BIIB092 in the study up to the last dose of BIIB092 treatment in the study plus 30 days.

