6.3.1 Quantitative analyses

Actual values, change from baseline and percent change from baseline will be summarized by visit for hematology, blood chemistry, coagulation (INR and prothrombin time), and the urinalysis parameters specific gravity and pH (actual values over time only), for all the visits in the active treatment (placebo-controlled and OLE) period. Number of evaluable subjects, mean, standard deviation, 25% and 75% quartiles, min and max values will be presented at each visit.

Plots of mean values (with standard error) for numeric laboratory parameters at each visit for all the visits in the active treatment (placebo-controlled and OLE) period will be provided. Mean values at timepoints where $n < 20$ will not be plotted.

Visit windows for by visit summaries

For laboratory by visit summaries, the analysis visit should be defined using visit windows (see Tables 7 and 8 below).

Table 7 Visit Windows for Laboratory by Visit Summaries for BIIB092 Early Start Subjects

| Analysis visit | Target visit day | Analysis visit window |
|-----------------------|-------------------------|---|
| Baseline | 1 | Most recent non-missing value prior to the first dose of study drug in the PC dosing period |
| Week 4 | 29 | [1 (post-dose only), 42] |
| Week 8 | 57 | [43, 70] |
| Week 12 | 85 | [71, 126] |
| Week 24 | 169 | [127, 210] |
| Week 36 | 253 | [211, 294] |

| Analysis visit | Target visit day | Analysis visit window |
|---|-------------------------|------------------------------|
| Week 48 | 337 | [295, 350] |
| Week 52 | 365 | [351, 406] |
| Week 64 | 449 | [407, 490] |
| Week 76 | 533 | [491, 616] |
| Week 100 | 701 | [617, 784] |
| Week 124 | 869 | [785,952] |
| Week 148 | 1037 | [953,1120] |
| Week 172 | 1205 | [1121,1288] |
| Week 196 | 1373 | >=1289 |
| Analysis Visit, Target visit day and Analysis visit window are calculated relative to the day of first dose of study drug (BIIB092 or placebo) in the PC dosing period. | | |

Table 8 Visit Windows for Laboratory by Visit Summaries for BIIB092 Late Start Subjects

| Analysis visit | Target visit day | Analysis visit window |
|--|-------------------------|--|
| OLE Baseline | 1 | Most recent non-missing value prior to the first dose of study drug in the OLE dosing period |
| Week 12 | 85 | [1 (post-dose only), 126] |
| Week 24 | 169 | [127 252] |
| Week 48 | 337 | [253, 420] |
| Week 72 | 505 | [421, 588] |
| Week 96 | 673 | [589, 756] |
| Week 120 | 841 | [757, 924] |

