6.1.2 Visit windows

Visit windows will be mutually exclusive, contain no gaps, and end at the midpoint between scheduled post-baseline visits, with the midpoint itself assigned to the subsequent visit window. If two or more evaluations occur in the same visit window, the evaluation closest to the target visit day will be selected for inclusion in the analysis. If multiple evaluations on different days are equally close to the target visit day, then the latest evaluation will be selected for inclusion in the analysis. If multiple evaluations occur on the same day, the earliest value will be chosen for analysis if time of collection is available; a scheduled value will be chosen before an unscheduled or early discontinuation record.

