6.4 ECGs

All individual values for QT interval, QT interval corrected for heart rate by Bazett's formula (QTcB), and QT interval corrected for heart rate by Fridericia's formula (QTcF) will be presented in the data listings. QT, QTcB, and QTcF will also be included in the summary statistics.

All available non-missing values of ECG parameters should be used in the listings, summaries, and analyses for the double-blind and open-label treatment periods. However, if QTcF is missing and RR interval in seconds is available, then QTcF will be calculated as

$$QTcF = \frac{QT}{RR^{1/3}}$$

If both QTcF and RR in seconds are missing, then QTcF will be calculated as

$$QTcF = \frac{QT}{(60/HEART\ RATE)^{1/3}}$$

Although all recorded ECG parameter values, including abnormal ECG findings, will be included in the data listings, only quantitative values recorded at or near scheduled time points will be included in the summary statistics (see Table 10).

Table 10 Visit Windows for ECG

| Analysis visit | Target visit day | Analysis visit window |
|---|------------------|---|
| Baseline | 1 | Most recent non-missing pre-dose value |
| Week 24 | 169 | [1 (post-dose only), 266] |
| Week 52 | 365 | [267, the end day of the placebo-controlled period *] |
| * The end day of the placebo-controlled period is the last day before the first dose in OLE for subjects who enter OLE, and is the last day in study for subjects who do not enter OLE. | | |

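### The placebo-controlled SAP closes the Week 52 lab and ECG windows the day before the first open-label dose, so values taken on the infusion day drop out of the randomized by-visit summaries

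*SAP*

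**What the plan says.** The placebo-controlled SAP, section 6.3.1, Table 8, gives the Week 52 laboratory window as "351, the end day of the placebo-controlled period". Section 6.4, Table 10, gives the Week 52 ECG window as "267, the end day of the placebo-controlled period". Both tables carry the same footnote: "The end day of the placebo-controlled period is the last day before the first dose in OLE for subjects who enter OLE". For participants who do not enter the OLE, the end day is their last day in the study. Section 6.1.2 requires windows without gaps.

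Protocol Table 2 schedules labs and ECG at Week 52 of the double-blind period. In the extension schedule (Table 3), the lab and ECG rows have no Week 52 entry; the Week 52 column carries dispensing of study treatment. Protocol 5.1.1 says that participants continuing into the extension "will receive the first dose of the open-label study treatment at Week 52".

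On the safety cut-off, protocol 17.4.2 says: "Safety endpoints will include data up to the start of the open-label extension period" for completers who continue. For late starters, the OLE SAP, section 6.3.1, Table 8, defines the laboratory baseline as "Most recent non-missing value prior to the first dose of study drug in the OLE dosing period".

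**The concern.** The cut-off works in whole days, but the Week 52 tests and the first open-label infusion belong to the same visit. When both fall on one day, that day lies outside the placebo-controlled period, including the hours before the infusion. The double-blind schedule calls for the test, yet the double-blind by-visit summary excludes the result.

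The OLE SAP does not restore the comparison. A dosing-day value from an early starter falls in that SAP's Week 52 windows. A pre-infusion value from a placebo participant becomes the late-start baseline instead. The randomized Week 52 by-visit comparison of labs and ECG exists only in the placebo-controlled SAP.

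The protocol schedules two post-baseline double-blind ECGs (Weeks 24 and 52) and seven post-baseline lab draws (Weeks 4, 8, 12, 24, 36, 48 and 52). A participant tested on the infusion day loses one of the two ECGs or one of the seven draws from the by-visit tables. If same-day testing is common, those left at Week 52 are weighted towards people who did not enter the OLE.

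**Working it through.** **Inputs**
- Target days 169 (Week 24), 337 (Week 48) and 365 (Week 52), and window starts of 351 for labs and 267 for ECG: placebo-controlled SAP, Tables 8 and 10.
- Midpoint rule, "with the midpoint itself assigned to the subsequent visit window": placebo-controlled SAP 6.1.2.
- Week 52 visit tolerance of ±3 days, and visits with efficacy assessments allowed to run over up to three consecutive days: protocol Table 2 and its footnote a.
- Expected Week 52 completers, 345 (230 BIIB092, 115 placebo): protocol 17.1.
- D = study day of the first OLE infusion. The window end is then D − 1.

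**1. Reproduce the plan's window starts.** Week 52 target: 52 × 7 + 1 = 365. Labs: (337 + 365)/2 = 351. ECG: (169 + 365)/2 = 267. Both match the tables.

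**2. Apply the end day.** With D = 365 the windows are [351, 364] for labs and [267, 364] for ECG. I tested every D from 362 to 368 (365 ± 3):

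| Test day | Lab window [351, D − 1] | ECG window [267, D − 1] |
|---|---|---|
| D (infusion day) | outside, all 7 values of D | outside, all 7 values of D |
| D − 1 | inside | inside |
| D − 2 | inside | inside |

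No other regularly scheduled visit fills the gap. Week 48 labs (337 ± 3 = 334 to 340) belong to the Week 48 window, and the Week 24 ECG (169 ± 3 = 166 to 172) to the Week 24 window.

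**3. Apply a time-of-dose end.** If the period ends at the first OLE infusion on day D, a value taken before the infusion that day is kept for all seven values of D.

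**4. Size.** Let r be the share of completers entering the OLE and s the share of entrants tested on day D. Both are assumptions, taken as equal in the two arms. Values dropped = 345 × r × s; values left per arm = 230 × (1 − rs) and 115 × (1 − rs).

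| r | s | Dropped | BIIB092 left | Placebo left |
|---|---|---|---|---|
| any | 0 | 0 | 230 | 115 |
| 0.7 | 0.5 | 120.75 | 149.5 | 74.75 |
| 0.8 | 0.8 | 220.8 | 82.8 | 41.4 |
| 0.9 | 1.0 | 310.5 | 23.0 | 11.5 |

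Section 6.3.1 does not plot lab means where n < 20. The placebo Week 52 point would disappear once rs exceeds 1 − 20/115 = 0.83, and the BIIB092 point once rs exceeds 1 − 20/230 = 0.91.

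**5. Selection.** The share of non-entrants among completers who keep a value is (1 − r)/(1 − rs):
- r = 0.7, s = 0.5: 0.30/0.65 = 46%, against 30% of all completers.
- r = 0.8, s = 0.8: 0.20/0.36 = 56%, against 20%.
- r = 0.9, s = 1.0: 0.10/0.10 = 100%, against 10%.
- s = 0: no distortion.

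**The case against.** Several points limit the reach of the finding, and most of them stand.

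- **A reader might infer that every OLE entrant loses the Week 52 value.** The text does not produce that. The visit may run over three days, and values from the day or two before the infusion stay in both windows.
- **A reader might infer that the protocol places these tests before the infusion.** It does not say so. Table 2 labels the physical examination as pre-dose and the targeted examination as post-dose but gives labs and ECG no timing. Footnote a requires only efficacy assessments before dosing. A post-infusion value is rightly excluded.
- **A reader might infer that the data are lost.** They are not. Listings cover the whole study (placebo-controlled SAP 3.1), and the OLE SAP uses dosing-day values: early-start windows of [351, 406] for labs and [267, 448] for ECG, and the late-start baseline if pre-dose. Week 48 labs remain in the randomized comparison. The affected summaries are descriptive, with no hypothesis test.
- **A reader might infer that the primary safety endpoint of Grade 3 and 4 laboratory abnormalities is truncated.** This is not established. Section 6.3.2 includes all values in the shift, grade and potentially clinically significant (PCS) analyses and states no end day. The categorical ECG analysis (6.4.2) uses each participant's maximum post-dose value, also with no stated end day.
- **Table 13 (anti-drug antibodies) has the same footnote.** No antibody sample is scheduled at Week 52 (protocol section 14), so no scheduled sample is removed.
- **Protocol 17.4.2 gives no clock time for the start of the extension.** That a pre-infusion value on the dosing day counts is the natural reading, but the protocol does not spell it out.

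None of this explains why a value taken before the first open-label infusion should be left out of the double-blind by-visit comparison.

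**Conclusion.** The point holds for participants who enter the OLE and have their Week 52 labs or ECG on the day of the first open-label infusion. Even if taken before the infusion, those values fall out of the only randomized Week 52 by-visit summaries. The rule is narrower than the natural reading of protocol 17.4.2. It leaves a gap that section 6.1.2 says should not exist, and it departs from the SAP's own practice of splitting Day 1 by dose time.

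ECG is affected most, since no other double-blind ECG is scheduled after Week 24; for labs, Week 48 remains. The number affected is 345 × r × s. The documents give neither share, so about 121 to 310 (r = 0.7 to 0.9, s = 0.5 to 1.0) is an illustration, and the true figure may be lower, down to zero. The selection effect depends on the same two shares. This is worth correcting before analysis, but it is not a threat to the efficacy analysis: the Week 52 efficacy windows have fixed ends and do not use this rule.

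**What to change.** In Tables 8 and 10 of the placebo-controlled SAP, end the placebo-controlled period for OLE entrants at the date and time of the first OLE infusion. Assign dosing-day values collected before the infusion to the placebo-controlled period. Where the collection time is missing, assign scheduled Week 52 labs and ECG to the placebo-controlled period, once the sponsor has confirmed that they are intended to be done before dosing; the schedule does not currently say so.

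Table 13 needs no change. The same cut-off may be stated for the Grade 3/4 and PCS counts for consistency, since section 6.3.2 gives none.

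The cost is a sentence or two of SAP wording, one confirmation from the sponsor and a programming rule. No new data are needed.

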6.3.2 Qualitative analyses

For all qualitative analyses, all values will be included (not just the “analyzed record” within each visit window in the quantitative analyses).

Shift analyses

Laboratory data will be summarized using shift tables where appropriate. Each subject’s hematology, blood chemistry, coagulation and urinalysis (excluding microscopic examination) values will be flagged as “low”, “normal”, or “high” relative to the normal ranges of the central laboratory or as “unknown” if no result is available. Each subject’s urinalysis values for protein, glucose, blood, and leukocyte esterase will be flagged as “abnormal” if positive, “normal” if negative, or “unknown” if no value is available.

For each parameter, the analysis will be based on subjects with at least one post-baseline value. Shifts from baseline to high/low status will be presented for hematology, blood chemistry, coagulation and urinalysis (specific gravity and pH), and shifts from baseline to abnormal (or unknown to abnormal) will be presented for urinalysis parameters (protein, glucose, blood, and leukocyte esterase). Shift to low includes normal to low, high to low, and unknown to low; shift to high includes normal to high, low to high, and unknown to high. Subjects need to have at least one post-baseline evaluation and a baseline value either unknown or not low/high/abnormal in order to be included in the analysis.

Grade analyses

Each scheduled laboratory parameter will be summarized both by worst post-baseline grade and by worst cumulative post-baseline grade; this analysis includes the primary endpoints of Grade 3 and 4 laboratory abnormalities. Subjects need to have at least one post-baseline evaluation in order to be included in the analysis. Common Terminology Criteria for Adverse Events v4.0.3 (CTCAE) published on 14 June 2010 will be used for grade determination. Grade determination is based solely on laboratory values and does not take other clinical information into account; therefore, a lower grade may be assigned to a laboratory parameter result since clinical information does not contribute to the grading assessment. Thus, the incidence of higher grades may be underestimated.

For calcium (mmol/L), the laboratory result will be corrected by the concurrent albumin (g/L) result for CTCAE grade determination. The derivation of the corrected calcium (mmol/L) will be derived as follows:

$$\text{Corrected calcium (mmol/L)} = \frac{1}{4} * [\text{calcium(mmol/L)} - 0.8 * (0.1 * \text{albumin(g/L)} - 4)]$$

Potentially Clinically Significant laboratory abnormalities analyses

For hematology, blood chemistry and urinalysis, the number of subjects with potentially clinically significant (PCS) laboratory abnormalities post-baseline will be summarized for the parameters provided in Table 9, which also shows the thresholds used to determine PCS results. Subjects need

to have at least one post-baseline evaluation and a baseline value not PCS (including missing) in order to be included in the analysis. A listing will be provided for subjects with any PCS result post-baseline.

Table 9 Criteria to Determine Potentially Clinically Significant (PCS) Laboratory Abnormalities

| Clinical Laboratory Outlier Criteria | | |
|---|----------------------------|----------------------------|
| Parameter name | PCS Low | PCS High |
| HEMATOLOGY | | |
| White blood cells | <3.0 x 10 ⁹ /L | >16 x 10 ⁹ /L |
| Lymphocytes | <0.8 x 10 ⁹ /L | >12 x 10 ⁹ /L |
| Neutrophils | <1.5 x 10 ⁹ /L | >13.5 x 10 ⁹ /L |
| Monocytes | N/A | >2.5 x 10 ⁹ /L |
| Eosinophils | N/A | >1.6 x 10 ⁹ /L |
| Basophils | N/A | >1.6 x 10 ⁹ /L |
| Red blood cells | ≤3.5 x 10 ¹² /L | ≥6.4 x 10 ¹² /L |
| Hemoglobin - Females | ≤95 g/L | ≥175 g/L |
| Hemoglobin - Males | ≤115 g/L | ≥190 g/L |
| Hematocrit - Females | ≤0.32 L/L | ≥0.54 L/L |
| Hematocrit - Males | ≤0.37 L/L | ≥0.60 L/L |
| Platelet count | ≤75 x 10 ⁹ /L | ≥700 x 10 ⁹ /L |
| BLOOD CHEMISTRY | | |
| Alanine aminotransferase (ALT) | N/A | >3 x ULN |
| Aspartate aminotransferase (AST) | N/A | >3 x ULN |
| Alkaline phosphatase (ALP) | N/A | >3 x ULN |
| Total bilirubin | N/A | >1.5 x ULN |
| Blood urea nitrogen (BUN) | N/A | ≥10.7 mmol/L |
| Creatinine | N/A | ≥176.8 umol/L |
| Sodium | ≤126 mmol/L | ≥156 mmol/L |
| Potassium | ≤3 mmol/L | ≥6 mmol/L |
| Chloride | ≤90 mmol/L | ≥118 mmol/L |
| Glucose | ≤2.2 mmol/L | ≥9.7 mmol/L |
| Calcium | ≤2 mmol/L | ≥3 mmol/L |
| Phosphorus | ≤0.6 mmol/L | ≥1.7 mmol/L |
| Albumin | ≤25 g/L | ≥625 g/L |
| Total protein | ≤45 g/L | ≥100 g/L |
| URINALYSIS | | |
| Glucose | N/A | ≥ 1000 mg/dL |
| Protein | N/A | ≥ 100 mg/dL |
| ULN = upper limit of normal | | |

Potential serious hepatotoxicity

Potential serious hepatotoxicity is defined as ALT or AST > 3x ULN and total bilirubin > 2x ULN at any time post-baseline, not necessarily concurrent. A scatterplot of the maximum post-baseline ALT or AST value relative to ULN and maximum post-baseline total bilirubin value relative to ULN (not necessarily concurrent) for each subject will be provided. A line plot of ALT, AST, ALP and total bilirubin values over time for subjects with potential serious hepatotoxicity will be provided. In addition, subjects with ALT > 1x ULN, >3x ULN, >5x ULN, >10x ULN or >20x ULN, subjects with AST > 1x ULN, >3x ULN, >5x ULN, >10x ULN or >20x ULN, subjects with total bilirubin >1x ULN or >2x ULN, subjects with ALP >1x ULN or >1.5x ULN, and subjects with AST or ALT > 3x ULN post-baseline accompanied by concurrently elevated total bilirubin >1.5x ULN or > 2x ULN will be presented. Concurrent is defined as on the same day. A listing of subjects with potential serious hepatotoxicity will be provided.

